4. ENDPOINTS

4.1. Co-Primary Efficacy Endpoints

The co-primary efficacy endpoints for this trial are as follows:

- Change from baseline (CFB) at Week 12 in average number of micturitions per 24 hours in all OAB patients
- CFB at Week 12 in average number of urge urinary incontinence (UUI) episodes per 24 hours in OAB Wet patients

For the purpose of this study, the number of micturitions will be defined as the number of times a patient has voided in the toilet as indicated on the Voiding Diary. Average daily micturitions are calculated using the daily entries in the Voiding Diary, which is completed prior to each study visit. Average daily number of micturitions will be calculated as the total number of micturitions that occur on a Complete Diary Day divided by the number of Complete Diary Days in the Voiding Diary. Unless a patient indicated “No” to the question of “Did you record each time you urinated or leaked during this Diary Day” the Diary Day is considered complete. Baseline is defined in [Section 6.3](#).

The number of UUI episodes will be defined as the number of times a patient has checked that they had "urge" as the main reason for the leakage, regardless of whether more than one main reason for leakage in addition to “urge” is checked. Average daily urge urinary incontinence episodes at each study visit will be calculated in the same manner as described above for the micturition endpoint. The urge urinary incontinence endpoint will be analyzed using only OAB Wet patients.

4.2. Key Secondary Efficacy Endpoints

The key secondary efficacy endpoints for this study are as follows:

- CFB at Week 12 in average number of urgency episodes (need to urinate immediately) over 24 hours in all OAB patients
- Percent of OAB Wet patients with at least a 75% reduction from baseline in UUI episodes per 24 hours at Week 12
- Percent of OAB Wet patients with a 100% reduction from baseline in UUI episodes per 24 hours at Week 12 (i.e., percent of OAB Wet patients with zero UUI episodes at Week 12)
- Percent of all OAB patients with at least a 50% reduction from baseline in urgency episodes (need to urinate immediately) per 24 hours at Week 12
- CFB at Week 12 in average number of total incontinence episodes over 24 hours in OAB Wet patients

- CFB at Week 12 in Coping Score from the OAB-q LF (1-week recall) in all OAB patients
- CFB at Week 12 in average volume voided per micturition in all OAB patients

4.3. Additional Secondary Efficacy Endpoints

The additional secondary efficacy endpoints for this study are as follows:

- CFB at Week 12 in Health-related Quality of Life (HRQL) Total Score from the OAB-q LF (1-week recall) in all OAB patients
- CFB at Week 12 in Symptom Bother Score from the OAB-q-LF (1-week recall) in all OAB patients
- Percent of all OAB patients with average number of micturitions < 8 per 24 hours at Week 12
- Percent of OAB Wet patients with at least a 50% reduction from baseline in total incontinence episodes per 24 hours at Week 12
- CFB at Week 12 in overall bladder symptoms based on Patient Global Impression of Severity (PGI-Severity) in all OAB patients
- CFB at Week 12 in overall control over bladder symptoms based on Patient Global Impression of Control (PGI-Control) in all OAB patients

4.4. Safety Endpoints

The following are the safety endpoints of this study:

[figure not shown]
- Incidence of adverse events
- Clinical Laboratory Assessments
- Vital Signs and Physical Examinations

[figure not shown]
4.5. Pharmacokinetic Endpoints

The PK objective of this trial is to evaluate the trough concentrations of vibegron in patients with symptoms of OAB. These concentrations may be used in combination with other data in a population PK model, which is beyond the scope of the analyses in this SAP. Vibegron concentrations in plasma over time will be summarized.

4.6. Exploratory Efficacy Endpoints

The exploratory efficacy endpoints for this trial are as follows:

5. ANALYSIS SETS

5.1. Screened Set

The Screened Set comprises all patients who signed the informed consent form (ICF) and have screening data entered into the database. This set includes screen failures, run-in failures, and randomized patients. For clarity, screen failure patients are those patients who fail to meet inclusion criteria or meet exclusion criteria and discontinued the study/withdrew consent prior to starting the Run-in treatment.

5.2. Run-in Set

The Run-in Set comprises all patients who entered the Run-in period of the study (i.e., were treated with at least one dose of the Run-in treatment). Patients will be considered run-in failures if they enter the run-in period (i.e. have at least one dose of run-in medication) but are not randomized to receive double-blind medication.

5.3. Randomized Set

The Randomized Set comprises all patients who were randomized to receive double-blind treatment after completing the Run-in period.

5.4. Safety Set

The Safety Set (SAF) will be used for the analysis of safety data for this study. The SAF consists of all patients who received at least one dose of double-blind study treatment. Patients will be included in the treatment group corresponding to the Study Treatment they actually received for the analysis of safety data using the SAF population. For most patients, this will be the treatment group to which they are randomized.

At least one laboratory or vital sign measurement obtained subsequent to at least one dose of study treatment is required for inclusion in the analysis of each specific parameter. To assess change from baseline, a Baseline measurement is also required.

No imputation will be performed for missing safety data (except for the case of partially missing dates in order to assign to study periods). Baseline will be defined as the last non-missing value before treatment.

5.5. Full Analysis Set

The Full Analysis Set (FAS) will serve as the primary population for the analysis of efficacy data in this study. Patients will be included in the treatment group to which they are randomized, regardless of which treatment they actually received, for the analysis of efficacy data using the FAS. Since the endpoints related to incontinence only apply to patients who meet the definition of incontinence at study entry, it is necessary to have a separate FAS definition with an additional criterion to define the primary analysis population for incontinence endpoints.

The following FAS populations are defined in the study:

- Full Analysis Set (FAS): all randomized OAB patients who took at least one dose of double-blind study treatment and have at least one evaluable change from baseline micturition measurement
- Full Analysis Set for Incontinence (FAS-I): all randomized OAB Wet patients who took at least one dose of double-blind study treatment and have at least one evaluable change from baseline UI measurement. The definitions of OAB criteria are presented in Protocol section 5.1.1 (Inclusion criterion 4), and [section 6.3](#) of this document.

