OAB Wet: Patients are considered OAB Wet according to the following criteria:

- An average of ≥ 8.0 micturitions per Diary Day; and,
- An average of ≥ 1.0 UUI episodes per Diary Day; and,
- If stress urinary incontinence (SUI) is present, the total number of UUI episodes must be greater than the total number of SUI episodes.

OAB Dry: Patients are considered OAB Dry according to the following criteria:

- An average of ≥ 8.0 micturitions per Diary Day; and,
- An average of ≥ 3.0 urgency episodes per Diary Day; and,
- An average of < 1.0 UUI episodes per Diary Day

OAB-d Type Missing: Patients are considered non-categorized for OAB if neither of the above criteria is achieved.

Where OAB Wet is discussed in this document, it pertains to patients randomized under the strata of OAB Wet; where all OAB Patients are discussed, this relates to all patients randomized as either OAB Wet or OAB Dry. Under the randomization strata, all patients are categorized as OAB Wet or Dry; missing is not present. Unless otherwise stated, for the purposes of the analyses, OAB Type (i.e. as randomized) will be used.

Diary Day

A “Diary Day” is defined as the time between when the patient gets up for the day each morning and the time the patient gets up for the day the next morning as recorded in the patient voiding diary.

Complete Diary Day

A “Complete Diary Day” is defined as a Diary Day that includes input of micturition data by patients on the voiding diary. Unless a patient indicated “No” to the questions of “Did you record each time you urinated or leaked during this Diary Day” the Diary Day is considered complete.

For post-baseline diaries at Weeks 4 and 8, only complete diary days within 10 days prior to the study visit will be included. For the Week 12/Early Termination diary, only complete diary days within 14 days prior to the study visit will be included. For the Week 2 diary, complete diary days within 10 days prior to the target Week 2 day will be used. For diaries at all visits, if a patient has fewer than 4 complete diary days, that will be identified as a significant protocol deviation and that diary data will be excluded from all analysis.

Definition of Baseline for Patient Voiding Diary Endpoints

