Baseline will be the data collected during the Run-in Period. If greater than 10 complete diary days are available in the Run-in diary, only the complete diary days within the 10 days prior to the Baseline visit will be used; if 4 or more and less than 10 complete diary days are available, all complete diary days in the Run-in diary will be used to calculate Baseline. If less than 4 complete diary days are available, the Baseline will be regarded as missing. For a patient to have an evaluable change from baseline, the patient must have both a baseline diary and a post-baseline diary from any post-baseline timepoint, after analysis window has been applied (i.e., Week 2, Week 4, Week 8, or Week 12).

Definition of Baseline for Endpoints not Derived from the Patient Voiding Diary

Baseline value for all secondary efficacy, exploratory and safety endpoints will be defined as the last non-missing assessment before starting double-blind treatment.

Screening/Washout Period

The Screening/Washout Period covers Day -49 (Screening Visit) to Day -15 (the day before the start of the Run-in Period), which includes a 28-day washout period followed by 7-days of Diary completion. Patients not requiring the 28-day washout period can begin the 7-day Diary the day after the Screening Visit.

Run-in Period

The Run-in Period covers the duration between screening (Day -14) and the day before baseline (Day 1). There is no day 0 included in the study.

Treatment Period

The Treatment Period covers the duration that a patient is in the study from Baseline (Day 1) and Week 12.

Safety Follow-up Period

The Safety Follow-up Period continues for 28 days after the last dose of study treatment (Day 85) through Day 113 (Follow-up Visit).

Definition of Study Completion

A patient will be defined as “completed” if she/he completes the Week 12 study visit.

End of Study Definition

End of study is defined as the date when the patient has completed one of the following: completed the follow-up visit after the Week 12 visit, enrolled into the extension trial 3004, permanently discontinued from the study, or lost to follow-up. When lost to follow-up, the latest date of assessment/event in the database will be used as the last known date of the patient in study.

Day of Study Event (Post-Randomization)

Day of study event = Event Date – Date of Randomization (Day 1) + 1.

Day of Study Event (Pre-Randomization)

Day of study event = Event Date – Date of Randomization (Day 1).

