8. EFFICACY ANALYSIS

Throughout the trial, patients were required to fill out an event and volume diary. It was intended for the patients to fill out the voiding diary for 7 days prior to the Run-in, Baseline, Week 2, Week 4, Week 8, and Week 12 visits, and to fill out the volume portion of the diary for 1 of the 7 diary days for each visit. Duplicate data recorded by the patient in diary rows with identical values will be not removed.

The definitions of a “Diary Day”, “Complete Diary Day”, and Baseline are given in [Section 6.3](#).

In order for a patient to have an evaluable change from baseline, the patient must have both a complete baseline diary and a post-baseline assessment from any post-baseline value (i.e., Week 2, Week 4, Week 8, or Week 12) for either micturitions for the FAS or UUI for the FAS-I. Change from baseline is defined as the post-baseline assessment minus the baseline assessment.

In general, the Full Analysis Set (FAS) will be used for all non-incontinence efficacy endpoints. The FAS-I will be used for all incontinence efficacy endpoints; these are the endpoints related to urge urinary incontinence (UUI) episodes and total incontinence episodes.

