The CFB analysis for the Coping Score will be calculated at Week 12 and analyzed in a similar manner as the primary endpoints, but with only one post-baseline assessment. More specifically, the primary inference will be drawn from the treatment difference between vibegron and placebo at Week 12 using a mixed model. The standard error and 95% CI for the difference will also be presented with the corresponding p-value. Additionally, estimates of least-squares means, standard errors, and 95% CIs will be presented for each treatment group and the difference between tolterodine and placebo will also be presented. The mixed model for this will use the same terms as the primary analysis, but without any repeated measures. An example of the SAS code for the base procedure is given below:

```
proc mixed data = datain method = reml ;
  class TRTP USUBJID OABTYPE SEX REGION ;
  model CHG = TRTP OABTYPE SEX REGION BASE
    / ddfm=KR solution chisq ;
  LSMEANS TRTP / pdiff=all cl alpha=0.05 ;
run ;
```

Where TRTP is the planned treatment, , USUBJID is the unique patient identifier, OABTYPE indicates of the patient is Dry or Wet, SEX is female or male, REGION indicates if the patient is in the United States or in non-US countries and BASE indicates baseline value.

The FAS will be the analysis population for the all of the OAB-q LF endpoints.

8.2.7. CFB in Average Volume Voided per Micturition at Week 12

Patients are asked to fill out a volume voided question for 1 day of the patient voiding diary. On this day, patients will use a graduated collection device to measure the volume of urine voided. Patients will collect this for every void on this 1 day. The average

volume voided at a visit will be the arithmetic mean of all voids for which a patient has recorded the volume. The CFB will be derived and analyzed in the same manner as described above in [Section 8.1.1.1](#). More specifically, the primary inference will be drawn from the treatment difference between vibegron and placebo at Week 12. The standard error and 95% CI for the difference will also be presented with the corresponding p-value. Additionally, estimates of least-squares means, standard errors, and 95% CIs will be presented for each treatment group. The table output will also include treatment group estimates and treatment differences between vibegron and placebo at Weeks 2, 4, and 8, as well as differences between tolterodine and placebo at Weeks 2, 4, 8 and 12 from this model.

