8.3.3. Patient Global Impression of Severity and Control

The Patient Global Impression (PGI) questions are designed to assess a patient’s overall impression of OAB, additional details are given in the [Appendix 3](#). The PGI-Severity and PGI-Control questions are ordinal assessments going from lower impact of disease to highest impact of disease with scales ranging from 1 to 4 for severity and 1 to 5 for control. These questions will be analyzed as categorical variables with count and percent for each category at Baseline, Week 4, Week 8, and Week 12. These questions will also be summarized descriptively as numerical variables of score and change from baseline at visits of Baseline, Week 4, Week 8, and Week 12. Finally, the change from baseline will be analyzed in the same manner using the MMRM described above in [Section 8.1.1.1](#).

[figure not shown]
[figure not shown]
The FAS will be the analysis set for the PGI analyses. For the MMRM analysis of change from baseline, no imputation of missing data will be performed.

[figure not shown]

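### FAS entry depends on the voiding diary, so a probably small number of patients with usable OAB-q or PGI data are left out of those questionnaire analyses

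*SAP*

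**What the plan says.** - **Entry to the FAS.** SAP 5.5 requires randomisation, at least one double-blind dose, and that patients "have at least one evaluable change from baseline micturition measurement".
- **What counts as evaluable.** Under 6.3, "the patient must have both a baseline diary and a post-baseline diary from any post-baseline timepoint". Section 8 repeats the condition, "for either micturitions for the FAS or UUI for the FAS-I".
- **Minimum diary content.** At any visit, "if a patient has fewer than 4 complete diary days, that will be identified as a significant protocol deviation", and that diary is left out of the analysis. For baseline, "If less than 4 complete diary days are available, the Baseline will be regarded as missing".
- **Questionnaire population.** Sections 8.2.6 and 8.3.1 both state: "The FAS will be the analysis population for the all of the OAB-q LF endpoints". Section 8.3.3 states: "The FAS will be the analysis set for the PGI analyses".
- **Status of the endpoints.** OAB-q Coping is sixth of the seven key secondary endpoints in 4.2, so it is in the formal testing sequence. OAB-q HRQL Total, Symptom Bother, PGI-Severity and PGI-Control are additional secondary endpoints (4.3), with nominal p-values only (6.2).

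**The concern.** The questionnaires do not rely on the diary. The notes to Table 3.11.1 have them administered at the site. Section 6.3 gives non-diary endpoints their own baseline, the last non-missing value before double-blind treatment. A patient can therefore have a usable questionnaire change and still be outside the only full analysis set available for it, because a different instrument was not completed.

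Part of that condition is met or failed after randomisation. Failure to produce any evaluable post-baseline diary could differ by arm, for example through early withdrawal. At stake are a little precision and a possible selection effect on one formally tested endpoint and four nominal ones.

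**Working it through.** **1. Who is excluded**

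Combining 5.5 with 6.3, a randomised and dosed patient is outside the FAS if either condition holds:
- the baseline diary has fewer than 4 complete days; or
- every one of the Week 2, 4, 8 and 12 diaries has fewer than 4 complete days.

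The first condition uses run-in data from before randomisation. It costs data but cannot be influenced by treatment. Only the second can bias the comparison.

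**2. Whether such a patient can have questionnaire data**

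Yes.
- Table 3.11.1 lists OAB-q and PGI under the combined Week 12 and early-withdrawal visit, and note 26 asks for the applicable Week 12 activities at withdrawal.
- Note 6 schedules the first post-baseline diary on days 8 to 14, and 6.5 opens the Week 2 diary window on Day 6. Four complete days from Day 6 are days 6, 7, 8 and 9, so a patient who leaves before about Day 10 will generally have no evaluable Week 2 diary.
- That patient's PGI falls in the Week 4 window of Table 6.5.1, which opens on Day 2. The OAB-q takes the scheduled visit recorded in the eCRF (6.5), so it is probably analysed as Week 12.

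**3. Whether another analysis brings the patient back**

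Not in the visible text. The PPS (5.6), supportive for the key secondary endpoints, is cut from the FAS. Section 6.4 specifies the MI and LOCF sensitivity analyses for the co-primary endpoints and uses no imputation for change-from-baseline analyses. MI for responders does not reach Coping or PGI.

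**4. The plan's own figures**

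The SAP states no power for OAB-q or PGI and no expected share outside the FAS, so there is no figure to reproduce on this point. The co-primary figures in 3.8 do reproduce, with power = Φ(δ / (σ√(2/n)) − 1.96):
- Micturitions: n = 450, δ = 0.6, σ = 2.20 gives 98.3% (stated 98%).
- UUI: n = 337, δ = 0.51, σ = 1.68 gives 97.6% (stated 98%).
- Both, if independent: 0.983 × 0.976 = 96.0% (stated 96%).

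A change of questionnaire population does not touch these.

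**5. Size of the precision loss (assumed range)**

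Let p be the share of about 500 per arm who are excluded, all with usable questionnaires. SE inflation = 1/√(1 − p) − 1.

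| p | Patients per arm | SE inflation |
|---|---|---|
| 1% | 5 | 0.5% |
| 2% | 10 | 1.0% |
| 4% | 20 | 2.1% |

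**6. Size of a possible shift (assumed)**

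If the treatment effect in the excluded patients differed by 0.5 SD from that in the others, the estimate would move by p × 0.5 SD: 0.005 SD at 1% and 0.02 SD at 4%. The SE of the difference at 450 per arm is √(2/450) = 0.067 SD.

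**The case against.** The other side has a good deal to say, and most of it stands.

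- **The bar for inclusion is low.** With a baseline diary, one evaluable diary at any of four visits is enough. The look-back is 10 days, or up to 14 at Week 12, and a day counts as complete unless the patient answers that it was not. Paper back-up diaries, reminders and retraining reduce failures further. This stands, and it is why the number is probably small.
- **The Coping data recovered may be of limited value.** An OAB-q completed at a very early withdrawal and analysed as Week 12 is a one-week-recall score from soon after randomisation, in a model without repeated measures. If it is not assigned to Week 12, the new set adds nothing for that patient. This stands as a limit on the gain.
- **The replacement set also filters after randomisation,** because it needs a post-baseline questionnaire. True, but that filter is on the instrument analysed, and a change-from-baseline analysis without imputation cannot avoid it. The diary filter is additional and avoidable.
- **FAS-I is a weak precedent.** Section 5.5 says "it is necessary to have a separate FAS definition with an additional criterion" because incontinence endpoints apply only to patients incontinent at entry. That is clinical applicability, not tailoring to an instrument. A closer parallel is 5.4, where inclusion in the safety analyses is decided parameter by parameter.
- **Imbalance would be visible.** Section 7.1 summarises set membership and reasons for exclusion by arm. That would show a difference but not correct it.

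A reader might infer that a patient with a poor Week 12 diary loses the Week 12 questionnaire. The SAP does not say so: any one earlier evaluable diary keeps that patient in the FAS. A reader might also infer that the SAP contradicts itself. It does not; 5.5, 8, 8.2.6, 8.3.1 and 8.3.3 are consistent, and a single FAS tied to a primary endpoint is a recognisable design choice.

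**Conclusion.** The point holds at minor severity. The SAP excludes from a key secondary endpoint and four additional secondary endpoints any randomised, dosed patient who has valid questionnaires but no evaluable diary micturition change, and no visible supportive analysis brings that patient back.

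The effect is probably small. The loss of 0.5% to 2.1% in precision assumes that 1% to 4% per arm are excluded and that every one of them has a usable questionnaire. The shift of 0.005 to 0.02 SD assumes a 0.5 SD difference in effect. None of these inputs comes from the SAP.

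It would be tempting to conclude that the Coping result is biased. The document does not support that: nothing in it shows that exclusion differs by arm, and the baseline condition cannot be affected by treatment. The co-primary analyses and their power are unchanged. The case for acting is that the exclusion has no stated reason for questionnaires and is cheap to remove.

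**What to change.** - In 5.5, add a questionnaire analysis set: all randomised patients who took at least one double-blind dose and have a baseline and at least one post-baseline value of the questionnaire being analysed, in the arm to which they were randomised.
- Name this set as primary in 8.2.6, 8.3.1 and 8.3.3. Keep the diary-based FAS for diary endpoints and as the supportive set for the questionnaires.
- Assign early-withdrawal questionnaires to visits by the rule already applied to FAS patients, so that the new set brings in no second convention.
- Make the change before unblinding, since a different questionnaire population chosen later would be post hoc.

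The cost is one definition, one population flag and three section edits. The downside is that questionnaire and diary tables will have slightly different denominators, which FAS-I already brings to the study for incontinence endpoints.
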